4.1. Full Analysis Set

The Full Analysis Set (FAS) is defined as all subjects who have been randomized and who have received at least one dose of treatment. Subject is assigned to the randomized treatment group regardless of actual treatment received. Analyses for endpoints that are defined based on a threshold of change from baseline (e.g. NRS4) will also require the baseline value to meet that threshold (e.g. for NRS4, the baseline value needs to be ≥ 4).

It is expected that the FAS as defined here will be identical to an ITT analysis set (randomized and dispensed study medication) because the first dose is administered in-clinic. The number of subjects randomized and dispensed study medication but did not receive treatment will be reported.

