5.2.1. Analyses of Binary Data

Binary data at each scheduled visit will be analyzed by two approaches: (1) the test of hypothesis (and the p-value) between the PF-04965842 treatment groups versus the placebo group will be conducted by the Cochran-Mantel-Haenszel (CMH) statistic adjusting for the effect of randomization strata; p-values from the CMH statistic will be used to establish the superiority of each dose of PF-04965842 to placebo in binary responses; and (2) the proportion of responders in the PF-04965842 treatment groups versus the placebo group will be summarized by the difference and its 95% confidence interval obtained by normal approximation. The difference in proportions will be calculated within each randomization stratum. The final estimate of the difference in proportions will be a weighted average of these stratum-specific estimates using CMH weights. The CMH weight w_k for stratum k ($k = 1, 2, 3, 4$) is given by,

$$w_k = \frac{\frac{n_{ik} n_{ck}}{n_{ik} + n_{ck}}}{\sum_{j=1}^4 \frac{n_{ij} n_{cj}}{n_{ij} + n_{cj}}}$$

where n refers to sample size, the subscript c refers to a comparator group (eg, placebo) and the subscript i refers to a test group (eg, either the low or high doses (so that two test statistics are calculated, one for each dose versus placebo). The difference is estimated as $\hat{d} = \sum_{k=1}^4 w_k (\hat{p}_{ik} - \hat{p}_{ck})$, where \hat{p} refers to the estimated relative frequency. An estimate for \hat{p} is obtained as x/n , where x is the number of responders.

Two-sided 95% confidence intervals for the difference (based on a normal approximation) are formed by:

$$\hat{d} \pm 1.96 \sqrt{\sum_{k=1}^4 w_k^2 \left(\frac{\hat{p}_{ik}(1 - \hat{p}_{ik})}{n_{ik}} + \frac{\hat{p}_{ck}(1 - \hat{p}_{ck})}{n_{ck}} \right)}$$

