5.2.3. Analyses of Longitudinal Continuous Data

Mixed-effect, repeated measures (MMRM) models will be used. The fixed effects of treatment (PF-04965842 200 mg QD and 100 mg QD and the placebo group), visit (Weeks 2, 4, 8 and 12), treatment-by-visit interaction and randomization stratification factors will be included. Visit will be modeled as a categorical covariate. Unstructured covariance matrix will be assumed for the model errors. Compound symmetry covariance matrix will be used if the model with unstructured covariance doesn't converge.

When modeling the change from baseline values, the variable for visit will start with the first post-baseline visit, and the actual baseline value will be included as a covariate. At each visit, estimates of least square mean (LSM) values and the LSM differences between the PF-04965842 treated groups and the placebo group will be derived from the model. The corresponding p-values and 95% confidence intervals will also be derived from the model.

Estimates of the difference in LSMs along with the two-sided 95% confidence interval will also be provided for the PF-04965842 200 mg QD group versus the PF-04965842 100 mg QD group. No hypotheses will be tested.

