5.3.1. Binary Endpoints

For binary endpoints analyzed at each scheduled visit separately, visit windows (see [Appendix 2](#)) will be used to map all observed data into nominal visits. After mapping, for subjects who drop out for any reason, any missing data will be defined as “non-responsive” from that point on at all subsequent visits; for other subjects, any observations missing intermittently (including baseline values) will be considered missing completely at random (MCAR) and will remain missing in the analysis.

Additional analyses that are based on statistical considerations will utilize the longitudinal nature of the binary endpoint. A Generalized Linear Mixed Model (GLMM) will be fit to the observed data (i.e., without defining missing data due to dropout as “non-response”). The binary outcome will be modeled using a logistic-normal distribution. Fixed factors will include treatment (PF-04965842 200 mg QD and 100 mg QD and the placebo group), visit (Weeks 2, 4, 8 and 12) and treatment-by-visit interaction. Visit will be modeled as a categorical covariate. A subject-specific random intercept will be used to model the correlation within a subject over time (see [Appendix 3](#)). Missing observations for the active groups will be imputed multiply using a tipping point analysis to estimate the treatment effect under the assumption that the missing data mechanism is missing at random (MAR) or more generally, is missing not at random (MNAR). Using the estimated posterior predictive distribution of the GLMM model parameters obtained using Markov Chain Monte Carlo (MCMC) methods, estimates of the posterior predictive probability of response will be calculated for each treatment group. For subjects with missing data at a visit, the posterior predictive response probability in each PF-04965842 dose group will be re-defined as a weighted linear combination of the posterior predictive response probability from this group and the posterior predictive response probability from the placebo group, where the missing observations in placebo group are assumed to be missing at random (MAR) (see [Appendix 3](#)). These weights are fixed MNAR quantities for the active groups. A single imputation of the missing value will be sampled from a Bernoulli distribution with this

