6.3. Key Secondary Efficacy Endpoints

6.3.1. Weeks 2, 4 and 12 NRS4 for severity Response

- Summary: Proportion of subjects with NRS4 for severity response at Week 2, 4 and 12.
- Population: Subjects from the FAS, PPAS with a baseline NRS score for severity ≥ 4 .
- Statistical Method: CMH and normal approximation in Section 5.2.1. Visit windows will be used as described in Appendix 2.
- Missing Data: Two analyses will be performed:
- Primary Analysis: Missing data arising due to subject dropout are considered “non-response”. For any other missing observations, a multiple imputation approach based on a GLMM will be used. (see the last two paragraphs within Section 5.3.1). This analysis will be based on both the FAS and the PPAS.

- Sensitivity Analysis: All missing data will be considered as “non-response”. This analysis will be based on the FAS only.

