Appendix 3. A Logit-Normal GLMM for Longitudinal Binary Data and Tipping Point Analysis

Appendix 4. A Logit-Normal Model

Let Y_{ij} be the binary outcome for subject i ($i = 1, 2, \dots, N$) and visit j ($j = 1, 2, 3, 4$). We assume $Y_{ij} = 1$ for a response and $Y_{ij} = 0$ for a non-response. Then we model as

$$P(Y_{ij} = 1 | x_{ij}, u_i) = \frac{e^{\beta' x_{ij} + u_i}}{1 + e^{\beta' x_{ij} + u_i}} \equiv \pi_{ij}(\beta; u_i)$$

Here, β is a vector of unknown parameters corresponding to the vector of fixed effects x_{ij} and u_i is a subject-specific random effect which is assumed to be normally distributed with mean 0 and variance σ^2 . Note that conditional on u_i , Y_{ij} is independent of Y_{ik} , when $j \neq k$.

The full marginal likelihood of the data is then,

$$L(\beta, \sigma^2) = \prod_{i=1}^N \int_{-\infty}^{\infty} \prod_{j=1}^4 \pi_{ij}(\beta; u_i)^{Y_{ij}} (1 - \pi_{ij}(\beta; u_i))^{(1-Y_{ij})} \times N(u_i; 0, \sigma^2) du_i$$

There is no closed analytical form for this likelihood.

For the present study, the primary endpoint is evaluated at Visit 8 / Week 12 ($j = 4$). There are three treatment groups, so the model term $\beta' x_{ij}$ when written out looks like,

$$\beta_0 + \sum_{k=1}^3 \beta_{1k} \times 1_{(T_i=k)} + \beta_{2j} + \sum_{k=1}^3 \beta_{3jk} \times 1_{(T_i=k)}$$

Here, T_i represents treatment for subject i . The third term in the expression is the effect for visit j and the fourth term in the expression is the interaction effect between treatment and visit. With an overall intercept term, the model is over-parameterized as written and so to fit the model, some restrictions on β are required. The default option (this can be changed using programming syntax) in standard statistical software is to assume $\beta_{13} = 0, \beta_{24} = 0$, thereby interpreting β_{11}, β_{12} as the difference in treatment effect relative to $T = 3$ and $\beta_{21}, \beta_{22}, \beta_{23}$ as the difference in visit effect relative to $V = 4$. Consequently, $\beta_{3jk} = 0$ when $j = 4$ or $k = 3$. So, for example, for a subject taking PF-04965842 100 mg QD at Week 12, the expression would be $\beta_0 + \beta_{11}$. For a subject taking PF-04965842 200 mg QD at Week 12, the expression would be $\beta_0 + \beta_{12}$. For a subject on placebo at Week 12, the expression would be β_0 .

Tipping Point Analysis

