A method to analyze the longitudinal data of a binary endpoint measured during the placebo-controlled period (e.g., IGA and EASI-75 response rates at Weeks 2, 4, 8 and 12) under the

MNAR assumption is called the tipping point analysis. This tipping point analysis includes two popular scenarios as special cases: (1) the Jump-to-Reference (JTR) analysis in which the response rate for a missing subject assessment in the active treatment group takes on (i.e., jumps to) the rate for the reference or control treatment group and (2) the MAR analysis in which the response rate for a missing subject assessment in each treatment group is based on the posterior predictive response rate for that treatment group alone.

The saturated logit-normal GLMM as described above will be used as the imputation model. Estimation of the model parameters will be performed under the Bayesian framework using Markov Chain Monte Carlo (MCMC) methods. We assign a non-informative prior for each component of β to be independent and identically distributed as $\sim N(0, 10000)$ and assign a weakly informative prior for σ^2 as an Inverse-Gamma distribution with shape=1 and scale=1. With this prior distribution, the 90th percentile for σ^2 is approximately 9.

Let $\beta^b, u_i^b, b = 1, 2, \dots, B$ be a sample from the posterior distribution. A single imputation $\widetilde{Y}_{i,j}^b$ of missing $Y_{i,j}$ is based on the posterior predictive distribution of the response probabilities estimated from the GLMM. For example, if subject i is randomized to PF-04965842 100 mg QD ($T_i = 1$), then at Week 12 ($V = 4$),

$$\text{logit}(\pi_{i,1,4}^b) = \text{logit}\left(P(\widetilde{Y}_{i,4}^b = 1 | T_i = 1, V = 4)\right) = \beta_0^b + \beta_{11}^b + u_i^b.$$

If subject i is randomized to PF-04965842 200 mg QD ($T_i = 2$), then at Week 12 ($V = 4$),

$$\text{logit}(\pi_{i,2,4}^b) = \text{logit}\left(P(\widetilde{Y}_{i,4}^b = 1 | T_i = 2, V = 4)\right) = \beta_0^b + \beta_{12}^b + u_i^b.$$

If subject i is randomized to placebo ($T_i = 3$), then at Week 12 ($V = 4$),

$$\text{logit}(\pi_{i,3,4}^b) = \text{logit}\left(P(\widetilde{Y}_{i,4}^b = 1 | T_i = 3, V = 4)\right) = \beta_0^b + u_i^b.$$

In the tipping analysis, we apply a series of fixed quantities $\delta = (\delta_1, \delta_2)'$ to account for MNAR. We define,

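### Does leaving the randomisation strata and baseline itch out of the model that imputes missing NRS4 values bias a key secondary analysis?

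*SAP*

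**What the plan says.** SAP 5.3.1 lists the fixed part of the imputation model: "Fixed factors will include treatment (PF-04965842 200 mg QD and 100 mg QD and the placebo group), visit (Weeks 2, 4, 8 and 12", then treatment-by-visit. A subject-specific random intercept carries the within-subject correlation. The logit-normal appendix (Appendix 3 in the contents list, sub-headed Appendix 4 in the body) writes out the predictor as intercept, treatment and visit, and adds that "the fourth term in the expression is the interaction effect between treatment and visit". It then states: "The saturated logit-normal GLMM as described above will be used as the imputation model". Saturated here means that every arm-by-visit rate is fitted freely, 3 x 4 = 12 of them. No other covariate appears.

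The confirmatory use is SAP 6.3.1, NRS4 at Weeks 2, 4 and 12. Dropouts count as non-responders, and "For any other missing observations, a multiple imputation approach based on a GLMM will be used". A second analysis on the FAS avoids the model: "Sensitivity Analysis: All missing data will be considered as" non-response.

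Three other places bear on the comparison:
- SAP 5.2.1, binary analysis: "The difference in proportions will be calculated within each randomization stratum".
- SAP 5.2.3, MMRM for continuous data: "treatment-by-visit interaction and randomization stratification factors will be included", together with the baseline value.
- SAP 4.1: analyses of change-threshold endpoints such as NRS4 "will also require the baseline value to meet that threshold".

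**The concern.** Multiple imputation under MAR is only as good as the variables it conditions on, and an imputation model is normally expected to hold at least what the analysis model holds. Here the values are drawn without regard to severity and age, and the completed data are then analysed within those strata. The MMRM in the same SAP carries both strata and baseline, so the omission looks like an oversight. NRS4 also depends on baseline by construction: a subject who enters at 4 must reach 0 to respond.

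If severity, age or baseline itch predicted both the loss of an NRS entry and the chance of response, beyond what arm and the subject's other visits reveal, the imputed responses would be drawn towards the arm average. NRS4 at Week 2 for 200 mg decides whether the later sequence is tested at 5% or 2.5%, so a material bias could reach confirmatory claims.

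**Working it through.** **1. Where the model enters.** The primary analyses of the co-primary endpoints (SAP 6.1.1 and 6.2.1) do not use it; only their supportive tipping-point analyses do. That leaves NRS4.

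**2. Mechanism.** SAP 5.3.1 describes an electronic transmission fault, not confined to any site or country and with no sign of a link to the pruritus or other endpoints. If that account is right, the data are MCAR and no covariate is needed for an unbiased difference.

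**3. Exposure at Week 2.** Protocol Schedule of Activities, footnote u: NRS is recorded daily to Day 15. SAP Appendix 2: the Week 2 window is Days 2 to 22, and the record closest to Day 15 is kept. A subject who lost only the Day 15 entry should still have a Week 2 value.

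**4. When imputation starts.** SAP 5.3.1 imputes nothing at a visit where every arm has five or fewer missing. 5/150 = 3.3% on an active arm and 5/75 = 6.7% on placebo. Take 40% severe (assumed) and loss of 2% in moderate and 6% in severe disease: 0.6 x 2% + 0.4 x 6% = 3.6%. That is 0.036 x 150 = 5.4 per active arm and 0.036 x 75 = 2.7 on placebo, just above the trigger.

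**5. Size of the bias.** The documents give no NRS4 rate and no count of lost values, so there is no plan figure to reproduce. Assumed Week 12 NRS4: 50% on 200 mg and 15% on placebo, a true difference of 35 points.

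SE = sqrt(0.5 x 0.5/150 + 0.15 x 0.85/75) = sqrt(0.001667 + 0.001700) = 5.8 points.

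A large-sample calculation fitted the planned model by marginal maximum likelihood and replaced missing Week 12 values by their predicted probability. Other assumptions: 20% adolescents; severity effect -0.5 or -1.5 on the logit; baseline effect -0.25 or +0.25 per point; random-intercept SD 1.5. Further truths lay outside the fitted family: severity-by-treatment and severity-by-visit effects, a quadratic baseline effect and a skewed random intercept. Week 2 is seen and later visits are lost unless stated.

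| Pattern of loss (moderate/severe unless stated) | Bias, points | Largest, in SE |
|---|---|---|
| MCAR 15% | 0.0 | 0 |
| 2%/6%, all arms | 0.0 to +0.1 | 0.14/5.8 = 0.02 |
| 5%/15%, all arms | 0.0 to +0.4 | 0.38/5.8 = 0.07 |
| 10%/30%, all arms | +0.1 to +0.8 | 0.84/5.8 = 0.14 |
| 10%/30%, all arms, Weeks 2, 4, 8 seen | 0.0 to +0.6 | 0.55/5.8 = 0.09 |
| 10%/30% by baseline NRS above 7 | -0.1 to +0.4 | 0.40/5.8 = 0.07 |
| Active arms only | +0.2 to +1.5 | 1.53/5.8 = 0.26 |

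A separate large-sample recomputation gave 0.00 for MCAR and 0.02 to 0.07 near the trigger. For 10%/30% it gave at most about 0.4, or 1.0 with an added severity-by-treatment effect (1.0/5.8 = 0.17 SE). The 10%/30% pattern means 0.6 x 10% + 0.4 x 30% = 18% of subjects lost; the SAP speaks of several subjects.

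**6. Simulation with multiple imputation and Rubin's rule.** Week 2, 150 trials per scenario, 15 imputations, normal approximation to the posterior. Shift from the full-data estimate in points; Monte Carlo error 0.15 to 0.25, SE of the difference about 6.

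| Scenario | Planned model | With strata and baseline |
|---|---|---|
| MCAR 10% | +0.01 | +0.08 |
| MCAR 20% | -0.30 | -0.39 |
| By severity, all arms, 10% | -0.27 | -0.30 |
| By severity, all arms, 20% | +0.02 | -0.35 |
| By severity, intermittent, 20% | +0.43 | +0.29 |
| Opposite directions by arm, 10% | +0.41 | -0.02 |
| Opposite directions by arm, 20% | +1.07 | +0.02 |

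Only the last two rows separate the models. They need severity to act in opposite directions on active and placebo, which a device fault in a double-blind trial gives no reason to expect.

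**7. False positives.** With 15% response in all arms, SE = sqrt(0.15 x 0.85 x (1/150 + 1/75)) = 5.05 points. A pattern common to all arms gives zero bias and 5.0% error. Active-only loss gives +0.14 to +0.74 points, hence 5.01% to 5.25% at the 5% level and 2.51% to 2.66% at the 2.5% level. These shift a complete-data SE by the bias and do not evaluate the Rubin-combined test. The simulated null rejection rates (Monte Carlo error about 2 points) are too coarse to tell the models apart: 9.3% against 8.7% under MCAR, 8.0% against 6.7% in the stress case, with full data at 7.3%.

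**8. What the covariates would buy.** Where the truth lies inside the enlarged model, the bias vanishes, which is circular. Outside it, the 10%/30% severity bias falls from +0.77, +0.81 and +0.84 to +0.44, +0.50 and +0.52; the first is (0.77 - 0.44)/0.77 = 43% removed, the others 38%. For loss by baseline NRS the three cases go from +0.07 to +0.10, +0.40 to +0.18 and +0.08 to +0.09, so two of three do not improve.

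**The case for a change.** The best case for the change is that the SAP claims MCAR or MAR, and if only MAR holds, the conditioning set matters. Its account of the fault mentions site, country and endpoints, but not severity, age or baseline itch. The covariates are already collected and cost two or three parameters. The all-missing-as-non-response analysis does not test the point: it makes a harsher assumption (27.7 to 33.9 points in the same scenarios, where the truth is 35) and does not examine whether MAR given arm and visits is adequate.

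Part of this stands. A richer model would make MAR plausible under more mechanisms, and the sensitivity analysis shows robustness to a pessimistic assumption rather than checking the imputation model. The rest does not carry. Nothing in the documents suggests a route from severity to device failure. The random intercept already brings in each subject's observed visits, which partly reflect severity. The MMRM is a weak comparator: it models continuous change, whereas NRS4 is analysed by CMH on severity and age only, so matching imputation to analysis would not call for baseline itch. The addition also has a price. With 20% adolescents, 75 x 0.2 = 15 placebo adolescents at 15% response give about 2 responders under vague priors, so a prespecified fallback sequence would be needed in a confirmatory analysis.

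**Conclusion.** The concern does not hold. The model omits the strata and baseline score, as read, but nothing the SAP states about it is wrong. Under the described device fault the bias is zero. Under severity-dependent loss common to all arms, which no section supports, it reaches at most about 1.0 point (0.17 SE), and near the imputation trigger about 0.1 point. A changed conclusion is unlikely. The five-subject rule, the Week 2 window and the non-response sensitivity analysis limit it further. These sizes rest on assumed response, covariate and missingness rates, and on maximum likelihood or a normal approximation in place of the planned MCMC. The conclusion would need revisiting if loss proved far heavier, or tied to severity differently by arm.

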5.1. Hypotheses and Decision Rules

PF-04965842 200 mg QD will be declared superior to placebo if the null hypothesis of no difference between PF-04965842 200 mg QD versus placebo for **both** co-primary endpoints is rejected at the 5% significance level. Similarly, PF-04965842 100 mg QD will be declared superior to placebo if the null hypothesis of no difference between PF-04965842 100 mg QD versus placebo for **both** co-primary endpoints is rejected at the significance level specified below.

A sequential Bonferroni-based iterative multiple testing procedure to strongly control the familywise Type 1 error at 5% will be used for testing each of the two PF-04965842 doses (200 mg QD and 100 mg QD) versus placebo on the primary and key secondary endpoints. The procedure belongs to a class of consonant multiple test procedures (Hommel et al. 2007) which are a subclass of the closed test procedures (Marcus et al. 1976).

[figure not shown]
The procedure will first test the Week 12 co-primary endpoints (IGA and EASI-75) for 200 mg QD vs placebo at a 5% significance level. If this hypothesis is not rejected, then no further testing will be conducted. If this hypothesis is rejected, then testing may continue on two paths depending on the testing for Week 2 NRS4 for severity for 200 mg QD vs placebo at a 2.5% significance level:

- If the hypothesis for the Week 2 NRS4 for severity for 200 mg QD vs placebo is rejected, then the unused alpha level of 2.5% will be passed on to a series of testing in

Sequence A (see Figure 2 below) at a 5% significance level. If any hypothesis in this sequence is not rejected, then the procedure stops.

- If the hypothesis for the Week 2 NRS4 for severity for 200 mg QD vs placebo is not rejected, then the series of testing in Sequence A (see Figure 2 below) will be tested at a 2.5% significance level. If any hypothesis in this sequence is not rejected, then the procedure stops. If all hypotheses in this sequence are rejected, then the unused alpha level of 2.5% will be passed on to the testing of hypotheses for Week 2 NRS4 for severity (200 mg QD vs placebo) at a 5% significance level.

Figure 2 Schematic for Multiple Testing Procedure

Hypotheses for all other endpoints not described here are to be tested at the nominal 5% significant level, without making adjustments for multiple comparisons.

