corresponding shifted / re-defined probability of response for the PF-04965842 dose groups. This imputation will be repeated multiple times with different MCMC samples to obtain multiple completed datasets. For each such completed dataset, the estimates of the proportions and CMH-weighted difference of proportions between each PF-04965842 dose group and placebo will be obtained along with the associated standard errors using the methods in [Section 5.2.1](#). Rubin's rule (Rubin, 1987) will be used to combine the multiple estimates and standard errors across the imputed datasets and provide p-values.

The above analysis can be repeated for different combinations of MNAR quantities which will be applied to the probability of response to assess when the conclusion might change (ie, tipping). Two important scenarios are included in the tipping point analysis framework. When the MNAR quantities are zero and the posterior predictive probabilities in the PF-04965842 dose groups are not shifted, results are obtained under an assumption of MAR for the missing data mechanism. Alternatively, at the other extreme, when the MNAR quantities are 1.0 for each PF-04965842 dose group, results are obtained under an assumption that the distribution of the missing responses after discontinuation of either dose of PF-04965842 is the same as that of the missing responses on the placebo arm. More detailed descriptions are provided in [Appendix 3](#).

Due to a technical error in the process of transmission and collection of electronic data with the device, the data on the pruritus NRS scale was not collected from several subjects at the scheduled visits of Week 2 (Day 15) and after. This was not restricted to a particular site or country and was not indicative of being related to the missing value of pruritus endpoint or any other endpoints. As such, the missing data mechanism may be reasonably assumed to be missing completely at random or missing at random.

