For the binary endpoints derived from the pruritus NRS, a hybrid approach will be used which is partially based on the multiple imputation method described in the previous paragraph. For this analysis, all data missing due to dropouts will be defined as "non-responsive" as described in the first paragraph, but any other data which remains missing at any intermittent visits will be handled using multiple imputation under the MAR assumption (which may be obtained by substituting the MNAR quantities as zero in the analysis described in the previous paragraph; see also, [Appendix 3](#)). At any particular visit, if there are 5 or fewer subjects with missing data in each treatment group after applying the non-responder definition, no imputations will be performed, and the data will remain missing. Note that, as described in the previous paragraphs, the GLMM will be fit to the observed data (ie, without defining missing data due to dropout as "non-response").

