9. APPENDICES

Appendix 1. Summary of Clinical Efficacy Analyses

Efficacy Endpoints	Population	Analysis Method	Missing Data Imputation	Primary Analysis for Co-primary Endpoints
Week 12 IGA Response	FAS	CMH	NR	Yes
	PPAS	CMH	NR	No
	FAS	CMH	TP(MAR)	No
	FAS	CMH	TP(MNAR)	No
Week 12 EASI-75 Response	FAS	CMH	NR	Yes
	PPAS	CMH	NR	No
	FAS	CMH	TP(MAR)	No
	FAS	CMH	TP(MNAR)	No
Weeks 2, 4, 8 and 12 NRS4 for severity Response	FAS	CMH	NR+MI	
	PPAS	CMH	NR+MI	
	FAS	CMH	NR	
Week 12 CFBL in PSAAD	FAS	MMRM	OD	
	PPAS	MMRM	OD	
Time to NRS4 for severity	FAS	Kaplan-Meier	OD	
Weeks 2, 4 and 8 IGA Response	FAS	CMH	NR	
Weeks 2, 4, 8 and 12 EASI-50/EASI-90/EASI-100 Response	FAS	CMH	NR	
Weeks 2, 4 and 8 EASI-75 Response	FAS	CMH	NR	
Weeks 2, 4, 8 and 12 %CFBL in Total EASI Score	FAS	MMRM	OD	
Days 1 – 15, Weeks 4, 8 and 12 CFBL in NRS for severity	FAS	MMRM	OD	
Weeks 2, 4, 8 and 12 CFBL in %BSA	FAS	MMRM	OD	
Weeks 2, 4, 8 and 12 %CFBL in SCORAD Total Score	FAS	MMRM	OD	
Weeks 2, 4, 8 and 12 SCORAD50/SCORAD75 Response	FAS	CMH	NR	
Weeks 2, 4, 8 and 12 CFBL in SCORAD subjective VAS assessments of itch and sleep loss	FAS	MMRM	OD	
CFBL=Change from baseline; CMH=Cochran-Mantel-Haenszel; GLMM=Generalized Linear Mixed Models; ANCOVA=Analysis of Covariance; MMRM=Mixed-effect Model Repeated Measures; NR=Non-Responder; TP=Tipping Point; MAR=Missing At Random; MNAR=Missing Not At Random.				

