$$\begin{aligned}\pi_{i,3,4}^{*b} &= \pi_{i,3,4}^b, \\ \pi_{i,1,4}^{*b} &= \delta_1 \pi_{i,3,4}^b + (1 - \delta_1) \pi_{i,1,4}^b, \\ \pi_{i,2,4}^{*b} &= \delta_2 \pi_{i,3,4}^b + (1 - \delta_2) \pi_{i,2,4}^b\end{aligned}$$

We then sample the single imputed value $\widetilde{Y}_{i,j}^b$ from a Bernoulli distribution with probability of success $\pi_{i,T_i,4}^{*b}$. For the present analysis, the responses from the placebo arm are not shifted.

Analysis of an imputed data set will produce an estimate as well as standard error of the treatment difference using CMH and normal approximation in [Section 5.2.1](#). For a given

value of MNAR parameter δ , this is repeated for B (typically, $B=500$) times to generate B complete imputed data sets and these B sets of estimates are combined using the Rubin's Method (Rubin, 1987). This can then be repeated for different values of MNAR parameter δ to evaluate the impact of missing data. Note that $\delta = (0, 0)'$ corresponds to an MAR analysis and $\delta = (1, 1)'$ corresponds to an analysis commonly known as Jump-To-Reference (JTR). As a special case, we will consider $\delta_1 = \delta_2$ for our analyses.

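### At visits where pruritus NRS data are imputed, the primary NRS4 p-value comes from a Rubin-combined unpooled Wald test instead of the stated CMH test, so a missing-data count decides which test is used at the Week 2 alpha gate

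*SAP*

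**What the plan says.** SAP 5.2.1 gives binary endpoints two separate tools. For the test, "p-values from the CMH statistic will be used to establish the superiority of each dose of PF-04965842 to placebo in binary responses". For estimation, it gives a CMH-weighted difference with an unpooled variance: "Two-sided 95% confidence intervals for the difference (based on a normal approximation) are formed by".

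SAP 5.3.1 then describes imputed data. Each completed dataset yields a weighted difference and its standard error by the 5.2.1 methods, and Rubin's rule "will be used to combine the multiple estimates and standard errors across the imputed datasets and provide p-values". The tipping-point text of SAP Appendix 3 (printed under a heading numbered Appendix 4) agrees: "Analysis of an imputed data set will produce an estimate as well as standard error of the treatment difference using CMH and normal approximation". Nowhere is a CMH chi-square pooled over imputations, and no reference distribution is given for the pooled statistic.

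This method, with the MNAR quantities set to zero, is carried into the pruritus endpoints. Under the primary NRS4 analysis in SAP 6.3.1, dropouts count as non-responders and "For any other missing observations, a multiple imputation approach based on a GLMM will be used". It applies visit by visit: "if there are 5 or fewer subjects with missing data in each treatment group after applying the non-responder definition, no imputations will be performed".

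SAP 6.3.1 and the Appendix 1 row "Weeks 2, 4, 8 and 12 NRS4 for severity Response" still name CMH as the method. In SAP 5.1, once the co-primaries pass, "then testing may continue on two paths depending on the testing for Week 2 NRS4 for severity for 200 mg QD vs placebo" at the 2.5% level.

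**The concern.** The test for one family of hypotheses changes with a count of missing records. At a visit with 5 or fewer missing in every group, the p-value is CMH. At a visit above that count, it is a Wald p-value with an unpooled standard error. NRS4 at Weeks 2, 4 and 12 could therefore be tested by different statistics, and the SAP does not say so.

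The two tests are not interchangeable under 2:1 allocation. The unpooled variance weights the placebo term by 1/75, so it shrinks when placebo response is low by chance. The CMH variance uses the combined response rate and does not shrink in the same way. When response rates are low to moderate, the switch therefore helps the drug.

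Week 2 NRS4 for 200 mg is where this matters most, because that result decides whether Sequence A is tested at 5% or 2.5%.

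**Working it through.** **Inputs from the documents.** 150 : 150 : 75 subjects; four randomization strata; the SAP 5.2.1 weights, variance and zero-responder rule; the 2.5% level from SAP 5.1; the more-than-5 trigger from SAP 5.3.1.

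**Assumed, because the documents give no value.** NRS4 response rates, stratum sizes and the missing fraction. Strata (active/placebo) were 81/41, 54/27, 9/4, 6/3, and alternatively 72/36, 48/24, 18/9, 12/6.

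**The plan's own figure.** No power or p-value is stated for NRS4. The nearest figure is IGA power of at least 95% (6% vs 26%). The pooled rate is (75×0.06 + 150×0.26)/225 = 0.193, giving a null SE of 0.0558 and an alternative SE of 0.0451. Power = Φ[(0.20 − 1.96×0.0558)/0.0451] = 97.8%, so the stated bound holds.

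**The two statistics.** In stratum k let h = n_a·n_c/(n_a+n_c), w = h/Σh, and d = Σ w(p_a − p_c).
- Wald: z = d / √Σ w²[p_a(1−p_a)/n_a + p_c(1−p_c)/n_c].
- CMH: z = T/√V, with T = Σ(x_a − n_a·m/N) and V = Σ n_a·n_c·m(N−m)/[N²(N−1)], where m is responders and N is subjects in the stratum.
- Since x_a − n_a·m/N = h(p_a − p_c), T = d·Σh. CMH is therefore the same weighted difference d divided by a null standard error, √V/Σh. Only the standard error differs.

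**Worked example, no imputation.** 20/150 vs 3/75, as 11/81, 7/54, 1/9, 1/6 vs 2/41, 1/27, 0/4, 0/3.
- h = 27.22, 18.00, 2.77, 2.00; Σh = 49.99.
- Stratum differences 0.0870, 0.0926, 0.1111, 0.1667; d = 0.0936.
- Wald: SE = 0.0375, z = 2.495, **p = 0.0126** (passes 2.5%).
- CMH: T = 4.677, V = 4.670, null SE = 0.0432, z = 2.164, **p = 0.0305** (fails 2.5%).

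Other splits at 2.5% in a single stratum: 36/150 vs 9/75 gives 0.0191 (Wald) and 0.0343 (CMH); 24/150 vs 5/75 gives 0.0247 and 0.0494. The direction can reverse at high response: 105/150 vs 42/75 gives 0.0408 and 0.0379.

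**False positives in the drug's favour at the two-sided 2.5% level (nominal 1.25%).** First strata set, 400,000 simulated null trials per rate, no imputation:

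| True rate | Wald | CMH |
|---|---|---|
| 10% | 1.90% | 0.91% |
| 15% | 1.93% | 1.01% |
| 20% | 1.87% | 1.07% |
| 30% | 1.75% | 1.15% |

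Over both strata sets and rates of 10–30%:
- Favourable tail at the 2.5% level: Wald 1.7–2.0%, CMH 0.9–1.2%.
- Favourable tail at the 5% level (nominal 2.5%): Wald 3.1–3.6%, CMH 1.9–2.4%.
- Wald two-sided size: about 2.6–3.1% at the 2.5% level and 5.1–5.8% at the 5% level.
- 0.6–1.0% of null trials pass the 2.5% gate by Wald only, and essentially none by CMH only.

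At a 5% null rate the Wald favourable tail is about nominal. At 2–3% it is below nominal (0.1–0.4%).

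**With imputation.** At null rates of 10–30%, with 5% or 10% missing, 50 imputations from a per-arm Beta posterior (a stand-in for the GLMM) and 12,000 runs per setting, the Rubin-combined Wald test gives:
- favourable tail 1.6–2.1% (2.5% level) and 2.9–3.6% (5% level);
- two-sided size 2.6–3.2% and 5.0–5.9%.

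Between-imputation variance does not remove the effect.

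**How often the trigger fires.** Six missing is 6/150 = 4% of an active arm or 6/75 = 8% of placebo. With the same missing rate in every arm, P(trigger) = 1 − P(X≤5 of 150)² × P(X≤5 of 75):
- 2% missing: 1 − 0.918² × 0.996 = 16%
- 3% missing: 1 − 0.704² × 0.975 = 52%
- 5% missing: 1 − 0.234² × 0.828 = 95%

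**The case against.** The best reply is that the rule is fixed in advance. SAP 5.3.1 says where imputed-data p-values come from, carries the method to the pruritus endpoints and sets the trigger, and SAP 6.3.1 refers back to it. A specific rule governs a general one. Appendix 1 also writes CMH against the tipping-point rows, whose p-values plainly come from Rubin's rule, so the label may be shorthand for the CMH-weighted difference. This has force: the Rubin p-value follows by cross-reference, and the gap may be one missing sentence. But the result is still two different tests for the same endpoint. If pooled CMH was intended, the SAP does not say how to pool it.

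The effect is also modest, and the example was chosen near the boundary. Using the co-primary planning rates as stand-ins, the tests disagree at 2.5% in 1.8% of trials (6% vs 26%) and 0.2% (15% vs 45%). With weaker effects they part more often: for 6 vs 18%, 10 vs 22%, 15 vs 30% and 20 vs 36% with 10% missing, Rubin-Wald alone is significant in 6.6–11.6% of trials and CMH on the observed data alone in at most 0.05%.

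The direction is not universal. At null rates of 2–5% the Wald test's two-sided size is below that of CMH, but this comes from the unfavourable tail. Wald's favourable tail was at or above CMH's at every null rate tried up to 50%. Near 70% the order reverses slightly.

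SAP 6.3.1 has a sensitivity analysis that counts all missing data as non-response and needs no imputation, so it keeps CMH. It also changes the missing-data assumption, so it does not isolate the effect of the test. Finally, the SAP attributes the missing diary data to a device error unrelated to outcome. That supports MAR but does not bear on which test is used.

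**Conclusion.** The concern holds. On the SAP's text, the primary NRS4 p-value is a Rubin-combined unpooled Wald test at imputed visits and CMH at the others, and the missing count settles which one applies at the Week 2 gate. At assumed null rates of 10–30%, the Wald test's favourable tail is at most about 1.6 times nominal at the 2.5% level (2.0/1.25), while two-sided size rises only slightly. No familywise error figure is claimed.

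The size of the effect rests on assumed NRS4 rates, strata and missing fractions, and on a simpler imputation model than the SAP's GLMM. The inconsistency itself rests on the text alone. The co-primary primary analyses are not imputed and keep CMH. The point should be corrected, but it does not undermine the design.

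**What to change.** State one p-value rule for NRS4 at all visits. In each imputed dataset, take d with its CMH null variance, V/(Σh)², combine by Rubin's rule, and name the reference distribution. Keep the unpooled variance for the confidence interval only. Because T = d·Σh, this returns the ordinary CMH p-value when nothing is imputed, so visits with and without imputation use the same test.

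In the imputation runs above, this rule gave a favourable tail of 0.9–1.2% at the 2.5% level and 2.0–2.5% at the 5% level, with two-sided size of 2.2–2.7% and 4.5–5.2%. Pooling CMH statistics by a Wilson-Hilferty transform is an alternative: favourable tail 1.0–1.25% and 2.2–2.6%, two-sided 2.4–2.9% and 4.8–5.5%.

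Align SAP 5.2.1, 5.3.1, 6.3.1 and Appendix 3, and make the change before unblinding. The cost is SAP wording and a small programming change. NRS4 p-values at imputed visits become slightly larger, and the p-value and interval can occasionally disagree there, as they already can at visits tested by CMH.
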